Objectives: This clinical protocol has the following three objectives: 1) *Develop a theory-based, guided mental imagery tobacco cessation intervention for quitline callers* with input from expert consultants in health disparities and a Community Advisory Board representing diverse populations and tobacco control stakeholders, 2) Develop training and competency standards for, and train, two imagery coaches in the implementation of the guided imagery intervention, and two behavioral strategy coaches for implementation of control condition, 3) Conduct a feasibility and acceptability trial (N= up to 120) to gather preliminary data on the effects of the guided imagery intervention on quitline callers' tobacco abstinence, number of quit attempts, number of cigarettes smoked, and self-efficacy to quit smoking.

Design and Outcomes

The study consists of two phases: 1) Developmental; and 2) Randomized Feasibility Trial.

Phase 1: As shown in Table 1 below, the development of the intervention will occur iteratively and include the following 7 stages: 1) the development of protocols for the guided imagery intervention and control conditions for use in a telephone-based coaching model; 2) a website containing instructions, and testimonials regarding the use of guided imagery and control conditions; 3) focus group testing of materials and the website (N=48); 4) the development of a training program for the study coaches; 5) Programming of the website and internal quality assurance/quality control (QA/QC) testing; 6) Usability testing of the study website; and 7) Modification of the ASHLine's 2.0 electronic data system to gather and transfer study information, and development of a REDCap system for protocol implementation, participant management and data storage.

Phase 2: Prior to beginning the trial, we will user test all recruitment and data collection systems with up to 10 user test participants to identify and correct any problems. We will randomize up to 10 user-test participants to test the ASHLine 2.0/REDCap systems and correct any errors identified. Once any identified errors are corrected, we will begin the feasibility trial. The Feasibility Trial will employ a two-group randomized controlled design. While developing the intervention, we will also develop an attention-control condition that will control for treatment length and contact time of the intervention. The trial will enroll up to 120 smokers (males and females age 18 and older) who will be randomly allocated to either the Imagery Intervention (IIC) or control condition (CC). Participants will be recruited and screened for eligibility by ASHLine staff and study staff. Informed consents and surveys will be obtained by ASHLine and study staff at baseline. Study staff will collect follow-up surveys at 8-weeks and 6-months postenrollment, including demographics, tobacco use, self-efficacy for quitting, cravings, and imagery expectancies for both groups. Participants will also complete measures of their imagery experiences, system usability, and other evaluations of their experiences with the website and study protocol. All participants who report abstinence at the 6-month assessment will be asked to perform a biochemical test using a saliva test kit to validate self-reported smoking abstinence. Participants meeting this criteria will be mailed a saliva kit in the mail and then join a video chat with staff who will instruct the participant and monitor the collection of saliva and reading of the test strip. Participants will be offered \$25 for completing the saliva assessment.

Commented [PG-(1]: Define abstinence: e.g. 7 day (not 30

Total participants to be enrolled for Phase 1 equal 48. Total participants to be enrolled in Phase 2 will be up to 10 user-test participants, and up to 120 feasibility trial participants. Total enrollment for all phases of this study will be up to 178.

The remainder of this protocol will describe procedures for the randomized feasibility trial.

Table 1. Project Timeline			
QLI Project Time Line	2016	2017	2018 2019
Activities Oct Nov Dec Jan Feb Mar	Apr May Jun Jul Aug Sei	Oct Nov Dec Jan Feb Mar Apr May Ju	Jul Aug Sep Oct Nov Dec Jan Feb Mar Apr May Jun Jul Aug Sep

Form IMC, hire																							
project staff, set																							
up accounts, set																							
up subawards																							
Develop																							
Protocols for																							
each study																							
conditions																							
Form Advisory																							
Board																							
Develop session								+												-			
content for each																							
study condition																							
Develop								+												-			
TrainingDesign																							
training manual																							
& competency																							
standards																							
Obtain feedback																							
on session																							
content from AB																							
and revise																							
Finalize study	\vdash					\forall	+	+			-	_	+	H	_				-	-	+		
measures																							
Get feedback																							
from AB and																							
revise measures																							
Identify all data								+													_	+	
items and																							
collection points																							
Develop																							
Website																							
Functional																							
specs, content,																							
user interface,																							
storyboards																							
Obtain feedback																							
from AB and																							
revise																							
Conduct Focus																							
Testing-Recruit																							
& conduct																							
groups & revise																							
website																							
Program																							
Website																							
Content & data																							
transfer, &																							
internal QA/QC																							
testing																							
Conduct	l T			ΙТ			T				Ī				T								
Usability																							
TestingRecruit																							
& conduct																							
testing, final																							
revisions to																							
website				Ш	\perp											L							
Customize											Ī				T								
		1	 						-		 												

ASHLine													
Software—													
Participant													
management,													
program													
management,													
data collection,													
data transfer													
Obtain feedback													
from QL													
coaches and													
revise													
Conduct													
usability testing													
and make final													
revisions													
Conduct													
Feasibility Trial													
Hire GI													
coaches													
Train all													
coaches													
Recruit													
participants,													
conduct user													
test													
Recruit													
participants,													
collect baseline													
data													
Collect data 8-													
week and 6-													
month data													
Analyze data													
Publications,													
presentations,													
finalize MOP													

Interventions and Duration

For the feasibility trial, we will randomize up to 120 participants to either the Imagery Intervention (IIC) or Control (CC) condition. We anticipate that participants will receive 6 sessions. All sessions will be approximately 20-50 minutes long. All participants will be instructed to log into the project website, which will contain a repository of study and intervention information tailored to condition.

Participants will be assessed at 8-weeks post-enrollment, and at 6 months post-enrollment via online survey (or phone for non-responders) by project personnel. All participants who report abstinence at the 6-month assessment will be asked to perform a biochemical test using a saliva test kit to validate self-reported smoking abstinence. Participants meeting these criteria will be invited to receive a saliva kit in the mail and then join a video chat with staff who will instruct the participant and monitor the collection of saliva and reading of the test strip. Participants will be offered \$25 for completing the saliva assessment.

Sample Size and Population

The target population for the feasibility intervention will be a racially and ethnically diverse sample of male and female smokers (N= up to 120) who will be randomized to the IIC or CC.

1. STUDY OBJECTIVES

1.1 Primary Objective

The primary outcome will be self-reported tobacco abstinence. We will measure 7-day point prevalence, 30-day point prevalence and prolonged abstinence at the 6-month follow-up assessment. All participants who report abstinence at the 6 month assessment and agree to perform a saliva test will be biochemically validated. We hypothesize that participants in the Imagery Intervention Condition will report equal or higher rates of cessation than those in the Control Condition.

Our feasibility outcomes include: at least 50% of participants will complete the 6-session intervention program; 50% Of the IIC participants will report listening to the guided imagery audio files at least 5 times per week; 50% will visit the website at least one time; and 75% of participants will complete both follow-up assessments.

1.2 Secondary Objectives

Secondary outcomes will include reduced tobacco use (for non-quitters), increased self-efficacy for quitting, and reduced nicotine cravings. We hypothesize that participants in the Imagery Intervention Condition will report equal or lower levels of tobacco use and cravings, and equal or higher levels of self-efficacy for quitting.

In addition, we will explore the demographics of study participants to assess how they may differ from the general population of ASHLine callers.

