dependence. All participants requesting NRT will be screened by trained project staff for contraindications for use, assessed for level of dependence, and informed of potential side effects (AEs and SAEs) of using NRT. The screening, assessment, and informational scripts are under development and will be submitted to the IRB for approval prior to these activities occurring with participants.

Participants will be assessed by project staff at 8-weeks and 6-months post-enrollment. Self-report surveys will be administered online or by phone. All participants who report abstinence at the 6-month assessment will be asked to perform a biochemical validation. Biochemical validation will be performed via saliva test kit sent to the participant's home and a video chat with University of Arizona project staff.

The primary outcome will be self-reported tobacco abstinence. We will measure 7-day point prevalence, 30-day point prevalence and prolonged abstinence at each follow-up assessment. We hypothesize that participants in the Imagery Intervention Condition will report equal or higher rates of cessation than those in the Control Condition.

Our feasibility outcomes include: at least 50% of participants will complete the 6-session intervention program; 50% will report listening to the guided imagery audio files at least 5 times per week; and 50% will use the website at least one time; and 75% of participants will complete both follow-up assessments.

Secondary outcomes will include increased number of quit attempts, reduced tobacco use (for non-quitters) and increased self-efficacy for quitting. We hypothesize that participants in the Imagery Intervention Condition will report equal or lower levels of tobacco use, and equal or higher levels of quit attempts and self-efficacy for quitting.

In addition, we will explore the demographics of study participants to assess how they may differ from the general population of ASHLine callers. Our goal is to increase the diversity of ASHLine callers.

[figure not shown]

Figure 1. Study Flow Diagram - Minimum Number of Participants Noted, Up to 120 (60 Per Condition) Will be Randomized

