Week 4-IIC (On or slightly before quit date)	Week 4-CC (On or slightly before quit date)
Theme: Handling withdrawal and preparing to quit	Theme: Handling withdrawal and preparing to quit
Goal: Determine strategies to handle withdrawals,	Goal: Determine strategies to handle withdrawals,
discuss use of NRT and quit preparation.	discuss use of NRT and quit preparation.
Content: Make edits or additions to script if	Content: Review strategies previously identified and
necessary. Practice entire script throughout week, or	any new ones, as needed.
just a portion if too long.	
Week 5-IIC	Week 5-CC
Theme: Relapse prevention/recommit to quit	Theme: Relapse prevention/recommit to quit
Goal: Support quitting among those who quit and	Goal: Support quitting among those who quit and
encourage quitting among those who didn't or who	encourage quitting among those who didn't or who
relapsed.	relapsed.
Content: Check whether participant wants any	Content: Revise behavioral strategies as needed to
changes to the script. If so, identify changes and re-	cope with anything that came up during the week.
record.	
Week 6-IIC	Week 6-CC
Theme: Relapse prevention/recommit to quit	Theme: Relapse prevention/recommit to quit
Goal: Prepare participants to be successful on their	Goal: Prepare participants to be successful on their
own. Give post-quit resources.	own. Give post-quit resources.
Content: Revise script if necessary. Provide GI and	Content: Revise behavioral strategies if needed.
relaxation resources.	
8 Week Follow-up Survey	8 Week Follow-up Survey
Assess for 7 day and 30 day point prevalence.	Assess for 7 day and 30 day point prevalence.
6 Month Follow-up Survey	6 Month Follow-up Survey
Assess for 7 day and 30 day point prevalence as well	Assess for 7 day and 30 day point prevalence as well
as prolonged abstinence.	as prolonged abstinence.

Participants are also eligible to use nicotine replacement therapy as per study guidelines. The study will provide nicotine lozenge or patch for up to 4 weeks if the participant has no medical contraindications for use.

Participants can opt in to receive text messages from the quit coaches throughout the quitting process. Quit coaches will ask participants during the coaching sessions if

they wish to receive additional, optional text messages (e.g., motivational messages, quitting tips, etc.).

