9.3 Definition of Populations

We will be using maximum likelihood based mixed models for all outcomes measured over time, using all available data. Mixed models are consistent with an intention to treat analysis due to their implicit imputation of missing data.

(Molenberghs et al., 2004). The per protocol population is defined as users who complete the 6-session intervention session.

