9.5.2 Secondary Outcomes

Secondary outcomes include number of quit attempts, number of cigarettes smoked, tobacco dependence, self-efficacy for quitting, and cravings. We will also explore the demographics of participants in the study compared to those of ASHLine callers in general.

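### Sections 1.2 and 3 limit the tobacco-use outcome to non-quitters while 9.5.2 does not; an arm comparison in non-quitters would not be a randomised one, though the expected bias is small

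*Combined protocol and SAP*

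**What the plan says.** Two places restrict the outcome. Section 1.2: "Secondary outcomes will include reduced tobacco use (for non-quitters), increased self-efficacy for quitting, and reduced nicotine cravings". Section 3 lists "increased number of quit attempts, reduced tobacco use (for non-quitters) and increased self-efficacy for quitting".

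Two places do not. The objectives in the Précis name "number of quit attempts, number of cigarettes smoked, and self-efficacy to quit smoking", and 9.5.2 reads: "Secondary outcomes include number of quit attempts, number of cigarettes smoked, tobacco dependence, self-efficacy for quitting, and cravings".

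The hypotheses that follow the restricted lists are between-arm statements without the restriction. In 1.2: "We hypothesize that participants in the Imagery Intervention Condition will report equal or lower levels of tobacco use and cravings". In section 3, imagery participants "will report equal or lower levels of tobacco use, and equal or higher levels of quit attempts and self-efficacy for quitting".

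On analysis, 9.3 says: "We will be using maximum likelihood based mixed models for all outcomes measured over time, using all available data". Besides that it defines only a per-protocol set. Section 9.6 plans mixed models for tobacco use, with arm contrasts at 8 weeks and 6 months. Neither section defines a non-quitter population, says which abstinence measure or time point makes someone a quitter, or says whether an abstainer counts as 0, as missing or as excluded.

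**The concern.** Whether a participant is a non-quitter is settled after randomisation, and it is the complement of the primary outcome. Sections 1.1 and 3 expect cessation to be equal or higher under imagery. If imagery raises quitting, and quitting is related to consumption or to readiness to quit, the people left smoking in the two arms are no longer comparable. A difference in their cigarette counts can then appear with no effect on the amount smoked. If quitting does not differ by arm, or is unrelated to consumption and readiness, there is no such bias.

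The more practical problem is that the outcome has two definitions. An analyst following 1.2 and one following 9.5.2 would estimate different quantities and could report opposite directions. The choice could also be made after the data are seen. Section 9.1 wants variance components for the future trial, and the variance of cigarettes smoked depends on whether abstainers enter as 0.

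**Working it through.** The plan gives no figure for this outcome, so there is none to reproduce. The check asks how far apart the two readings are and how large the selection bias could be.

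**Inputs from the documents.** At least 50 per arm and 20% dropout (9.2.1), so 50 × 0.8 = 40 completers per arm. Abstinence of 12% v 26% comes from a smaller in-person imagery trial cited in 2.2 and is used as the upper scenario.

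**Assumptions, not in the documents.** Lower scenarios of 12% v 12% and 12% v 19%. Baseline cigarettes/day gamma-distributed with mean 15 and SD 8. Lighter smokers quit more, with log-odds slope 0.3 to 1.0 per SD. Imagery has no effect on the amount smoked by anyone who continues.

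**Step 1. Non-quitters only, follow-up level.** Imagery minus control, cigarettes/day (simulation, 1,000,000 per arm; repeat runs agree within 0.02):

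| Quit rates | Slope 0.3 | 0.5 | 0.8 | 1.0 |
|---|---|---|---|---|
| 12% v 12% | 0.00 | -0.01 | 0.00 | 0.00 |
| 12% v 19% | +0.15 | +0.22 | +0.33 | +0.39 |
| 12% v 26% | +0.31 | +0.49 | +0.71 | +0.83 |

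With slope 0 the difference is within 0.02 of 0. All of this is selection, and it runs against imagery.

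**Step 2. All randomised, abstainers scored 0.** Let p0 and p1 be the quit rates, m0 the control non-quitter mean and d the non-quitter difference. Then

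all-randomised difference = -(p1 - p0) × m0 + (1 - p1) × d.

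With slope 0, m0 = 15 and d = 0. This gives -0.07 × 15 = -1.05 at 12% v 19% and -0.14 × 15 = -2.10 at 12% v 26%. With slopes 0.3 to 1.0 the simulated values are -0.95 to -0.76 and -1.92 to -1.57. The sign is opposite to Step 1. This is mostly the quit difference multiplied by about 15 cigarettes; it is a different estimand, not an error.

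**Step 3. Bias against precision.** Non-quitters number 40 × 0.88 = 35.2 (control) and 40 × 0.74 = 29.6 (imagery). SE for level = 8 × √(1/35.2 + 1/29.6) = 2.0. Largest ratio: 0.83 / 2.0 ≈ 0.4 SE, so a nominal two-sided 5% test has a size of about 7%. With 60 per arm (48 completers; 42.2 and 35.5 non-quitters) the SE is 1.82 and the ratio 0.83 / 1.82 = 0.46.

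**Step 4. Change from baseline or baseline adjustment.** For change, for baseline adjustment, and for a mixed model with baseline as a time point (the plan does not say whether it is one), the bias is within 0.02 of 0. It returns only if an unmeasured factor drives both quitting and consumption. The assumed readiness factor has log-odds 0.3 to 1.0 per SD and 2 to 3 cigarettes/day per SD, with follow-up noise SD 5. It leaves +0.02 to +0.18 at 12% v 19% and +0.04 to +0.33 at 12% v 26%. The SE for change is 1.34 to 1.45, so the largest ratio is about 0.2 SE (0.33 / 1.45 = 0.23, size 5.6%).

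**Step 5. Sensitivity.** A separate set of assumptions used baseline SD 7, continuing smokers at 80% of baseline in both arms, slopes 0.5 to 1.5, and 12% v 26%. It gave +0.36 to +0.81 in non-quitters and -1.47 to -1.19 in all randomised.

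**Step 6. Do the zeros upset the remedy?** In 4,000 simulated trials per cell (equal quitting of 12% to 26%, 40 or 48 per arm, baseline-adjusted linear model at one time point), size was 4.7% to 5.7% with ordinary SEs and 4.5% to 5.4% with robust SEs. The mixed model with both follow-ups was not simulated.

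**The case against.** The strongest reply is that no non-quitter comparison is planned. The statistical section points the other way: 9.5.2 has no restriction, 9.3 uses all available data and defines no non-quitter set, and 9.6 excludes no one. Section 6.2.4 adds that every participant is asked every item at each follow-up, and an abstainer's natural answer is zero. The parenthesis in 1.2 and 3 may be a loose label for a reduction outcome. This stands in large part. A reader might infer from 1.2 that the trial is committed to a biased arm comparison; the documents do not support that. They show an unresolved conflict between outcome lists, with the scoring of abstainers left unstated.

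It is also fair that the restricted outcome is worded as a reduction, for which the bias is near zero without the added readiness factor. The 12% v 26% contrast comes from in-person imagery added to counselling, whereas this trial uses an attention control matched for contact time. And because the bias runs against imagery, the 7% is not a risk of a false benefit claim: at 0.4 SE the tail favouring imagery falls from 2.5% to about 0.9%.

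What remains is that 1.2 and 3 pair the restricted outcome with a between-arm hypothesis, and nothing in 9.3 or 9.6 settles which population applies or how abstainers count.

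**Conclusion.** The point holds as an inconsistency in one secondary outcome. The restricted reading, if used to compare arms, loses the protection of randomisation; the unrestricted reading keeps it. The two can differ in sign if imagery raises quitting, although the non-quitter expectation is well under 1 SE from zero.

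The expected selection bias is small: about 0.4 SE at most for an unadjusted level with 50 per arm, near zero for change or with baseline adjustment, and about 0.2 SE if an unmeasured readiness factor of the assumed strength exists. These sizes rest on assumed consumption, slopes and quit differences. With equal quitting, or quitting unrelated to consumption and readiness, the bias is zero. A reader might take the gap between the two readings as the size of the error; it is not, because they estimate different things. No primary or feasibility result depends on this. The correction is worth making because the definition is open and costs little to close.

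**What to change.** In 1.2 and 3, delete the parenthesis limiting the outcome to non-quitters. In 9.5.2, replace the cigarette item with text such as:

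*Cigarettes per day at 8 weeks and 6 months in all randomised participants. Participants reporting 7-day point-prevalence abstinence at that assessment are scored 0; non-responders are left missing. The arms are compared with the linear mixed model of 9.6, adjusted for baseline cigarettes per day, with robust standard errors. Reduction among participants still smoking at that assessment is described by arm without a between-arm test.*

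The abstinence definition can be applied at each visit because Table 2 in 5.1 specifies it for both follow-ups ("Assess for 7 day and 30 day point prevalence"). Name this one model rather than a choice of models.

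Also make 9.1 consistent with 9.5. Section 9.1 calls tobacco use the primary efficacy outcome and lists only dependence, cravings and self-efficacy as secondary, while 9.5.1 names cessation at 6 months as primary.

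Cost: wording in four sections and no new data. The downsides are that the outcome partly overlaps with cessation, reduction among continuing smokers is not formally tested, and smokeless use by dual users (admitted under 4.1) is not counted, as under the present 9.5.2 wording.
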